Several validated questionnaires exist for capturing the overlap of GI symptoms in the general population and for categorizing them into specific groups based on most likely GI diagnoses. The validated questionnaires most cited and often used by the National Institutes of Health (NIH) and accepted by the FDA for purposes of clinical drug trials are the ROME IV questionnaires(11), Patient Assessment of Gastrointestinal Symptoms (PAGI-SYM)(12), Patient-Assessment of Constipation Symptoms (PAC-SYM)(13) and Patient- Assessment of Constipation Quality of Life (PAC-QOL)(14).

ROME IV is used as a diagnostic tool for what was previously termed “Functional Bowel Diseases”; however, it does not stratify patients based on symptom intensity and was purely formed for diagnostic purposes. It is a long and laborious set of questionnaires and although also validated in children more than 4 years of age, its limitations include the inability to analyze symptom severity. In contrast, the PAC-SYM is a 12-item questionnaire that evaluates many different GI symptoms including nausea, vomiting, upper or lower abdominal pain, constipation and other questions related to stool habits(13). A higher score corresponds with worse symptoms; with a range from 1 to 4 points. In the general adult population, a decrease in score of about 1 point indicates moderate improvement and a decrease of about 0.5 points indicating minimal improvement. Another validated scale system is the Bristol Stool Scale discussed above(9, 15) which is primarily based on a pictorial identification of stool consistency and validated both in the pediatric and adult population. A lower score on the Bristol Stool Scale (Type 1 and 2) corresponds with harder stool, whereas a higher score suggests diarrhea (Type 6, 7) with total range of scores ranging from 1 to 7.

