Stool Symptoms (NN=nn)									
PAGI-SYM Total Score (NN=nn)									
Nausea/Vomiting (NN=nn)									
Post-Prandial Fullness/Early Satiety (NN=nn)									
Bloating (NN=nn)									
Upper Abdominal Pain (NN=nn)									
Lower Abdominal Pain (NN=nn)									
Heartburn/Regurgitation (NN=nn)									
PAC-QOL Total Score (NN=nn)									
Physical Discomfort (NN=nn)									
Psychosocial Discomfort (NN=nn)									
Worries and Concerns (NN=nn)									
Satisfaction (NN=nn)									

A.5 Summary of Prevalence and Variability of GI Symptoms

Exhibit 5.1.1 Summary of Disease-Specific Questionnaire – All Participants

This table summarizes the GI disease-specific questionnaire for all participants. All questions were based on patient's experience in the last week.

		Baseline (N=n)	Week 1 (N=n)	Week 2 (N=n)	Week 4 (N=n)
Bowel Movements	<3 Bowel Movements ≥3 Bowel Movements		n (%)		
Self-Described Bowel Pattern:	Normal Constipated Diarrhea Alternating Constipation and Diarrhea				
Bristol Stool Scale ^[1] :	1 (Hard Lumps) – 2 3 – 5 6 – 7 (Watery) Missing				
Leakage of Stool:	Yes				
Protocol-Defined Constipation ^[2]:	Yes				

[1] Question for Bristol Stool Scale: describe what your stool looked like on most days in the last week when you had a bowel movement?

[2] Protocol-defined constipation is defined as less than 3 bowel movements and/or Bristol Stool type 1 or 2 in the past week

Exhibit 5.1.2 Summary of Disease-Specific Questionnaire – Age < 18

Exhibit 5.1.3 Summary of Disease-Specific Questionnaire – Age ≥ 18

Exhibit 5.2.1 Demographics and Baseline Characteristics by Protocol-Defined Constipation at Baseline.

This table summarizes demographics and baseline characteristics, stratified by protocol-defined constipation at Baseline Visit.

	Protocol-Defined Constipation at Baseline		All Enrolled Participants (N=n)	Fully Completed at Least One ePRO at all Follow-up Weeks (N=n)	CF Registry (N=n)
	Yes (N=n)	No (N=n)			
Sex at Birth, n (%)	Female				
	Male				
Age Distribution, n (%)	<6 years				
	≥6 – 12 years				
	≥12 – 18 years				
	≥18 – 24 years				
	≥24 – 30 years				
	≥30 years				
	Mean (SD)				
	Median				
	Min, Max				
Race, n (%)	White				
	American Indian or Alaska Native				
	Black or African American				
	More than One Race				
	Unknown or Not Reported				
Ethnicity, n (%)	Hispanic or Latino				
	Not Hispanic or Latino				

CF Therapeutics Development Network Coordinating Center
GALAXY-OB-18

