Symptom Presence [3], n (%)					
Symptom Score [4], mean (sd)					
Symptom 2					
N [2]					
Absent, n (%)					
Mild, n (%)					
Moderate, n (%)					
Severe, n (%)					
Very Severe, n (%)					
Symptom Presence [3], n (%)					
Symptom Score [4], mean (sd)					

[1] Overall results were aggregated over all participants weeks. Overall symptom score is obtained from a longitudinal model.

[2] Number of participants who completed the question at each week

[3] Symptom presence is defined as checking any severity level other than "Absent"

[4] Symptom score is defined based on the scoring rubric of each ePRO (max of 4 for PAC-SYM and PAC-QOL, and max of 5 for PAGI-SYM)

Note: Selected symptoms were prespecified from PAC-SYM, PAGI-SYM, and PAC-QOL questionnaires (see Appendix C for the complete list of prespecified symptoms of interest). Scoring of symptoms range from either 0-4 (PAC-SYM and PAC-QOL) or 0-5 (PAGI-SYM)

Exhibit 5.3.2 Summary of GI Symptoms from PAC-SYM, PAGI-SYM, and PAC-QOL – Age < 18 Years
Exhibit 5.3.3 Summary of GI Symptoms from PAC-SYM, PAGI-SYM, and PAC-QOL – Age ≥ 18 Years

Exhibit 5.4.x Change from Baseline for [GI Symptom]

The following table shows the change in distribution for each symptom (including stool frequency/type) from baseline at each follow-up week.

		Week 1 (N =) [1] (Mean Score = , 95% CI =)						Week 2 (N =) [2] (Mean Score = , 95% CI =)						Week 4 (N =) [3] (Mean Score = , 95% CI =)																
		Absent		Mild		Moderate		Severe		Very Severe		Absent		Mild		Moderate		Severe		Very Severe		Absent		Mild		Moderate		Severe		Very Severe
Baseline (Mean = , 95% CI =)	n (%) Worsened	n (%)		n (%)		n (%)		n (%)		n (%)		n (%)		n (%)		n (%)		n (%)		n (%)		n (%)		n (%)		n (%)		n (%)		
		Moderate	Mild	Absent	Very Severe	Severe	Moderate	Absent	Very Severe	Severe	Moderate	Absent	Very Severe	Severe	Moderate	Absent	Very Severe	Severe	Moderate	Absent	Very Severe	Severe	Moderate	Absent	Very Severe	Severe	Moderate	Absent	Very Severe	
		n (%) Improved				n (%) No Change				n (%) Improved				n (%) No Change				n (%) Improved				n (%) No Change								

[1] Consider participants with both baseline and Week 1 data

[2] Consider participants with both baseline and Week 2 data

[3] Consider participants with both baseline and Week 4 data

Note: One table per each symptom; PAC-QOL only has data for Baseline and Week 4

Exhibit 5.4 Change in GI Symptoms from Baseline

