The following table shows the changes in GI symptoms from baseline at each follow-up week. This is a collapsed version with less details compared to the 5.4.x exhibits.

GI Symptom	Baseline Mean (95% CI)	Week 1					Week 2					Week 4				
		N [1]	Mean (95% CI)	Worsen – n (%)	No Change – n (%)	Improved – n (%)	N [1]	Mean (95% CI)	Worsen – n (%)	No Change – n (%)	Improved – n (%)	N [1]	Mean (95% CI)	Worsen – n (%)	No Change – n (%)	Improved – n (%)
Symptom 1	Mean (95% CI)	n	mean (CI)	n (%)	n (%)	n (%)	n	mean (CI)	n (%)	n (%)	n (%)	n	mean (CI)	n (%)	n (%)	n (%)
Symptom 2																
...																
Symptom s																

[1] N per each follow-up week is defined as the number of participants who had data at both baseline and the follow-up week.

Exhibit 5.5.1 Summary of PAC-SYM, PAGI-SYM, and PAC-QOL Total Score by Protocol-Defined Constipation

This figure summarizes the distribution of total scores for PAC-SYM, PAGI-SYM, and PAC-QOL by **weekly** protocol-defined constipation status

[figure not shown]
[figure not shown]

Exhibit 5.5.2 Summary of PAC-SYM, PAGI-SYM, and PAC-QOL Total Score by Self-Defined Constipation

Similar figure to Exhibit 5.5.1 but using self-defined constipation.

Exhibit 5.6.1 Model-based Summary of PAC-SYM, PAGI-SYM, and PAC-QOL Total and Domain Scores by Protocol-Defined Constipation

This figure provides model-based summaries of the total and domain scores, for all participants and by weekly protocol-defined constipation. The estimates are obtained from mixed-effect models with participant-specific random intercepts, as well as fixed effects for protocol-defined (weekly) constipation status, week, and age group. The predictor of interest is constipation status.

Exhibit 5.6.2 Model-based Summary of PAC-SYM, PAGI-SYM, and PAC-QOL Total and Domain Scores by Self-Defined Constipation

Similar figure to Exhibit 5.6.1 but using self-defined constipation.

A.6 Summary of Alternative CF-Specific Definitions of Constipation

Exhibit 6.1.x Summary of PAC-SYM total score by constipation status defined by [protocol or specific rules]

This figure (one figure per one definition of constipation) shows how the distribution of PAC-SYM total score looks with different definition for constipation, and an in-sample ROC curve constructed by using PAC-SYM total score in a longitudinal model as a classifier for the corresponding weekly constipation status.

[figure not shown]

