Exhibit 7.1 Summary of Treatment for GI Symptoms and Constipation at Baseline

This table summarizes the number of participants initiating treatment, receiving treatment (along with the medication type/class), or neither at baseline.

	Age Category		All Enrolled Participants (N=n)
	Age < 18 (N=n)	Age ≥ 18 (N=n)	
Neither Initiating nor Receiving Treatment	n (%)		
Initiating or Receiving GI Treatment			
Type of Treatment			
Non-Constipation			
Medication 1			
...			
Medication m			
Constipation			
Medication 1			
...			
Medication m			
Route			
GI Tube			
Others			
Note: missing data			

Note: See Appendix D for a list of GI medications of interest. GI/Constipation medications were derived from all concomitant medications based on ATC coding.

Exhibit 7.2 Summary of GI Symptoms and Constipation by Receiving Constipation Treatment

This table summarizes GI symptoms and constipation status at baseline by receiving constipation treatment.

	Receiving Constipation Treatment	
	Yes (N = n)	No (N = n)
GI Symptoms	Symptom 1 (n = x) Symptom 2 (n = x) ... Symptom s (n = x) Any Symptom (n = x)	
Protocol-Defined Constipation	Yes (n = x)	
Self-Defined Constipation	Yes (n = x)	
Other Definition of Constipation	Definition 1 (n = x) Definition 2 (n = x) ... Definition d (n = x)	

Note: missing data

Note: See Appendix B for a list of prespecified alternative definition of constipation.

Exhibit 7.3.x.y Change in [GI Symptom X] from Baseline among [Subgroups Defined by Constipation Treatment at Baseline]

This table is similar to the 5.4.x tables for each subgroup defined by constipation treatment at baseline (initiating/receiving or neither). The table shows the change in distribution for each symptom X (including stool frequency/type) from baseline at each follow-up week.

		Week 1 (N =) [1] (Mean Score = , 95% CI =)						Week 2 (N =) [2] (Mean Score = , 95% CI =)						Week 4 (N =) [3] (Mean Score = , 95% CI =)					
Baseline (Mean = , 95% CI =)	n (%) Worse	Absent	Mild	Moderate	Severe	Very Severe		Absent	Mild	Moderate	Severe	Very Severe		Absent	Mild	Moderate	Severe	Very Severe	
		Absent	n (%)	n (%)				n (%)	n (%)					n (%)	n (%)				
		Mild	n (%)					n (%)						n (%)					
		Moderate						n (%)						n (%)					
		Severe						n (%)						n (%)					
		Very Severe						n (%)						n (%)					
		n (%) Improved					n (%) No Change	n (%) Improved					n (%) No Change	n (%) Improved					n (%) No Change

[1] Consider participants with both baseline and Week 1 data

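### The SAP's change tables put Bristol stool type, a scale abnormal at both ends, into a one-directional Worsened/Improved severity grid with a mean score

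*SAP*

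**What the plan says.** SAP Appendix A.5, Exhibit 5.4.x, is the per-symptom change table: "The following table shows the change in distribution for each symptom (including stool frequency/type) from baseline at each follow-up week". Appendix A.7, Exhibit 7.3.x.y, uses the same layout within subgroups defined by constipation treatment at baseline: "The table shows the change in distribution for each symptom X (including stool frequency/type) from baseline at each follow-up week".

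In both, baseline is crossed with each follow-up week on five ordered levels from Absent to Very Severe. The margins count participants who worsened, improved or did not change, and a mean with 95% CI is printed for baseline and each week. The note to 5.4.x reads "Note: One table per each symptom; PAC-QOL only has data for Baseline and Week 4"; no separate layout for stool items appears. Exhibit 5.4 summarises these tables ("This is a collapsed version with less details compared to the 5.4.x exhibits"), and Exhibit 7.3 does the same for 7.3.x. Both keep the mean and the three counts but do not name the stool items.

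On the Bristol scale, Protocol 1.2 says that types 1 and 2 mean harder stool, "whereas a higher score suggests diarrhea (Type 6, 7) with total range of scores ranging from 1 to 7". SAP Exhibit 5.1.1 groups it in three bands: "1 (Hard Lumps) – 2 3 – 5 6 – 7 (Watery) Missing".

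Scores are defined in Exhibit 5.3.1 only for the three scored questionnaires: "max of 4 for PAC-SYM and PAC-QOL, and max of 5 for PAGI-SYM". Neither document defines a score, or a direction that counts as worse, for Bristol type or stool frequency.

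**The concern.** A Worsened/Improved grid needs an outcome that runs from good to bad. Bristol type runs from one abnormal end, through a middle band, to the other abnormal end, so no ordering of the seven types gives every change its proper sign. The mean has the same weakness, because opposite extremes cancel.

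These tables deliver the endpoint on change in stool frequency and type: protocol endpoint 9, and SAP items 12 (overall) and 20 (by GI treatment at baseline). The treated versus untreated tables matter most. If constipation treatment loosens stool, then with lower counted as worse, a treated participant who moves from the middle band to watery stool is counted as Improved. With higher counted as worse, relief of hard stool is counted as Worsened. Either error would then fall more heavily on the treated group, in a study with a stated objective of informing treatment algorithms.

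**Working it through.** The documents give no figure on this point, so there is none to reproduce. Four checks follow.

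**1. All possible changes of type.** Seven types give 7 x 6 = 42 ordered changes. Judge each by whether it moves nearer to or further from the 3-5 band (distance 2, 1, 0, 0, 0, 1, 2 for types 1 to 7).

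| Ordering | Labelled wrongly | Labelled rightly | Given a direction though distance is unchanged |
|---|---|---|---|
| Higher = worse | 16 | 16 | 10 |
| Lower = worse | 16 | 16 | 10 |

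Measured from type 4 instead, the counts are 18, 18 and 6 under either ordering. These are counts of table cells, not of participants.

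**2. Share of between-band changes labelled wrongly.** Let h be the share in types 1-2, l the share in types 6-7 and n = 1 - h - l, and assume that the two visits are independent. Then:

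- higher = worse: wrong share = hn / (hn + ln + hl)
- lower = worse: wrong share = ln / (hn + ln + hl)
- the remainder, hl / (hn + ln + hl), crosses between extremes and has no natural direction.

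Inputs: h = 20% to 30%, borrowed from the constipation prevalence in Protocol 15.7. This is only a proxy, since that figure is a one-month period prevalence and also counts fewer than 3 movements. The documents do not give l; it is assumed to be 2% to 30%.

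| h | l | n | hn | ln | hl | Sum | Wrong, higher = worse | Wrong, lower = worse |
|---|---|---|---|---|---|---|---|---|
| 25% | 5% | 70% | 0.1750 | 0.0350 | 0.0125 | 0.2225 | 79% | 16% |
| 25% | 20% | 55% | 0.1375 | 0.1100 | 0.0500 | 0.2975 | 46% | 37% |
| 30% | 2% | 68% | 0.2040 | 0.0136 | 0.0060 | 0.2236 | 91% | 6% |
| 20% | 30% | 50% | 0.1000 | 0.1500 | 0.0600 | 0.3100 | 32% | 48% |

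Over the whole range the wrong share is 32% to 91% with higher = worse, and 6% to 48% with lower = worse.

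**3. Net direction in one assumed scenario.** Baseline is 25% hard, 60% middle and 15% loose. Of the hard and of the loose, 40% move to the middle; of the middle, 10% move to hard and 8% to loose.

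- Moved into the middle: 0.25 x 0.40 + 0.15 x 0.40 = 0.100 + 0.060 = 16.0%.
- Moved out: 0.60 x 0.10 + 0.60 x 0.08 = 0.060 + 0.048 = 10.8%.
- Higher = worse: improved 0.060 + 0.060 = 12.0%, worsened 0.100 + 0.048 = 14.8%. The net direction reverses.
- Lower = worse: improved 0.100 + 0.048 = 14.8%, worsened 0.060 + 0.060 = 12.0%. The net direction is kept.

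**4. Mean, frequency and PAGI-SYM levels.**

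- Half the participants at type 1 and half at type 7 have mean (1 + 7)/2 = 4, the same as everyone at type 4.
- For frequency, Exhibit 5.1.1 uses fewer than 3 against 3 or more, and Appendix B adds fewer than 7 as an alternative definition. No upper abnormal limit is set, so no two-ended mislabelling follows.
- PAGI-SYM items are scored 0-5, which is six levels, while the grids in Exhibits 5.3.1, 5.4.x and 7.3.x.y have five. Appendix C lists 3 PAC-SYM and 8 PAGI-SYM symptoms, so 8 of the 11 scored symptoms do not match the grid.

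**The case against.** The strongest defence is that the layout is a placeholder. Absent to Very Severe cannot literally be rows for Bristol type, so some adaptation is implied, and the SAP nowhere states a one-directional rule for stool items. That stands against any claim that a wrong rule has been specified. It does not remove the gap: the SAP's preface promises detailed table specifications, and without one the ordering is left to whoever programs the table.

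Several stronger readings are tempting but unsupported:

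- A reader might infer that a large share of stool changes will be mislabelled. The direction is unstated and the frequency of types 6-7 unreported, so neither a large nor a small share is shown.
- A reader might infer that the tables would reverse the net direction of change. In the scenario above this happens under one ordering only. The other, lower = worse, is arguably the more natural choice here, since types 1-2 define constipation.
- A reader might extend the two-ended argument to stool frequency. The documents give no upper limit to support that.
- A reader might infer that changes in PAGI-SYM items will be lost by merging levels. The SAP proposes no merge and states the six-point scale elsewhere; this is a minor layout mismatch.

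It is also fair that the full cross-tabulations would show individual transitions despite poor margin labels, and that Exhibit 5.1.1 already gives the three bands by week. Exhibits 6.3.1, 6.4.x and 6.5.x relate treatment to constipation with clear directions. None of those, however, tracks movement to loose stool by treatment. Exhibits 5.4 and 7.3 include stool items only by implication.

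**Conclusion.** The point holds for Bristol type. Exhibits 5.4.x and 7.3.x.y place it in a severity grid with Worsened/Improved counts and a mean, and any single ordering gives some changes the wrong sign. The mean can hide opposite extremes. This rests on reading 3-5 as the band to move towards, which follows from the protocol's description of the two ends and the SAP's own grouping.

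The size cannot be fixed from the documents. The range of roughly 6% to 91% of between-band changes depends on the ordering chosen, the assumed shares at each end and independence between visits. For stool frequency the defect is only that direction and score are undefined.

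The consequence is confined to descriptive secondary endpoints, SAP items 12 and 20. The primary endpoint, the sample size and the period prevalence of constipation are untouched.

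**What to change.** - **Bristol type:** remove it from the severity grid in Exhibits 5.4.x and 7.3.x.y, and from 5.4 and 7.3 if it was meant to appear there. Report a 3x3 shift table on the SAP's bands (1-2, 3-5, 6-7) for each follow-up week, overall and by baseline constipation treatment. Summarise it as moved into 3-5, moved out to 1-2, moved out to 6-7, crossed between extremes, and no change in band. Give no mean.
- **Stool frequency:** report shifts across the SAP's stated cut-offs (fewer than 3, and fewer than 7 as the alternative definition), without a severity mean.
- **PAGI-SYM items:** use six levels in Exhibits 5.3.1, 5.4.x and 7.3.x.y.

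The cost is an edit to the SAP's table layouts and one or two extra layouts to program. No new data are needed.
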